### **Data management**

All study information will be securely stored in the Clinical Research Laboratory, Department of Kinesiology, Universidad Católica del Maule, Chile, in locked cabinets. The information of each patient will be classified by means of numerical codes and will be kept 5 years after the end of the investigation in closed filing cabinets. Access to the information will be limited to people outside the research team of this study.

### **Statistical Analysis**

Statistical analysis will be performed using a statistical package SPSS (version 17.0). The data will be expressed as mean, standard deviation (SD), lower and upper limit of the confidence interval (CI, 95%) or median, minimum, maximum, first and third quartile, according to normality distribution using the Kolmogorov Smirnov test. To assess fatigue, symptoms of urinary incontinence, sexual function and quality of life, a two-way mixed analysis (two-way ANOVA) will be performed, considering time (pre-intervention and post-intervention) as an intra-subject and group factor as a between-subjects factor. The significance level will be set at .05 for all statistical analyses. The intragroup effect sizes for the aforementioned variables will also be calculated using the Cohen d index. An effect size of more than 0.8 will be considered large, approximately 0.5 moderate, and less than 0.2 small (Cohen, 1988).

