### **Determination of sample size**

The sample size was calculated using the GPower version 3.1 software, considering a size of effect, Cohen's  $d$  of 0.2, to achieve a power of 80%, with a significance level of 5%. was used the analysis of variance of repeated measures, considering interaction between and within groups using 2 measurements. Thirty-six participants (18 per group) were suggested.

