### **Generation and hiding of sequences**

After selecting the sample and performing the baseline evaluations, the participants will be randomly assigned to one of the two study groups. Randomization will be performed by a member of the team, blinded to the study protocol. A computer program will be used to perform the randomization (<https://www.graphpad.com/quickcalcs/randomize1.cfm>). Both groups will receive 4 weeks of supervised training with a frequency of three times a week, with an approximate duration of 60 minutes each session. Figure 1 presents the flowchart with the experimental design of the study.

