### **Data collection**

Standardized forms will be used to record pre- and post-intervention evaluations. The registry will consider demographic data, social and health habits, clinical variables: comorbidities, blood pressure, body mass index (weight, height), type of gynecological cancer, cancer staging and type of oncological treatment. In addition, the dosage of the kinesthetic intervention will be recorded according to the Borg scale for each session.

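### The planned two-time-point mixed ANOVA is a valid change-score test, but ANCOVA on the baseline already collected would usually be more precise, by an amount set by the unstated pre-post correlation

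*Combined protocol and SAP*

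**What the plan says.** The Statistical Analysis section covers fatigue, urinary incontinence symptoms, sexual function and quality of life with one model: "a two-way mixed analysis (two-way ANOVA) will be performed, considering time (pre-intervention and post-intervention) as an intra-subject and group factor". Group is the between-subjects term. Baseline enters only as one level of the time factor; no covariate is named. The section does not say which ANOVA term tests the treatment, and the only effect sizes it plans are within group. The sample-size section does point to a term: it "was used the analysis of variance of repeated measures, considering interaction between and within groups using 2 measurements", and it arrives at 36 women, 18 per group.

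Three other places bear on the point:

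- The section on how the allocation sequence is made and concealed puts baseline first: "After selecting the sample and performing the baseline evaluations, the participants will be randomly assigned to one of the two study groups". Baseline therefore cannot be affected by allocation.
- Data collection: "Standardized forms will be used to record pre- and post-intervention evaluations".
- Blinding (masking): a blinded physical therapist assesses the outcomes at both times.

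No pre-post correlation and no outcome SD is stated anywhere.

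**The concern.** The change score subtracts the whole baseline value, as if the slope of post on pre were exactly 1. With equal SDs the slope equals the correlation r, which is below 1. Subtracting too much adds baseline noise to the comparison; ANCOVA estimates the slope and removes that noise. The trial pays for the baseline measurement in either case.

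With 18 women per arm and no stated allowance for dropout there is little slack. Both arms do the same strength and resistance sessions, and the hypopressive component is the only addition, so the conclusion rests on how precisely the difference between arms is estimated.

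**Working it through.** **Inputs from the documents.** 18 per arm (N = 36), two groups, two measurements, effect size 0.2, 80% power (Determination of sample size); alpha 0.05 (Statistical Analysis).

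**Assumptions.** r is unstated, so a range is shown. SDs are unstated; they are taken as equal across arms and times and set to 1, and the equality over time is relaxed in step 6. Power figures also assume normal data and a common linear slope.

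**1. The plan's own figure.** For the group-by-time interaction, λ = f²·N·2/(1−r) with 1 and N−2 df.

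- With f = 0.2 and r = 0.5, 52 women are needed for 80% power, and 36 give 64.5%. N = 36 is recovered only near r = 0.65 to 0.66.
- If 0.2 is d and is converted to f = 0.1, N = 36 is recovered only near r = 0.91.

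So the stated N cannot be reproduced without supplying an r that the plan does not give. That is a separate matter, but it indicates which values of r would fit the plan.

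**2. The planned test.** In a 2×2 mixed design the interaction F equals the squared t for the difference in mean change. A numerical check gave 1.21878 for both. Simulated type I error at 18 per arm was 0.050 to 0.051 for the change score and 0.049 to 0.051 for ANCOVA.

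**3. Variances of the estimated difference between arms.**

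- Change score: 2(1−r)·(2/18), 34 df.
- ANCOVA: (1−r²)·(2/18)·[1 + 1/(N−4)], 33 df. The last factor, 1 + 1/32 = 1.031, is the average cost of estimating the slope.
- Ratio: (1−r²)/[2(1−r)] × 1.031 = (1+r)/2 × 1.031.

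At r = 0.5 the ratio is 0.75 × 1.031 = 0.77, which is worth 36/0.773 ≈ 47 women.

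**4. Results at N = 36.** Power is for a 0.8 SD difference, which is what f = 0.2 means in a 2×2 interaction: f = δ/(4 SD), so δ = 4 × 0.2 = 0.8 SD.

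| r | Variance ratio | Equivalent N | 95% CI half-width in SD, change / ANCOVA | Power, change / ANCOVA | Total N for 80% power, change / ANCOVA |
|---|---|---|---|---|---|
| 0.3 | 0.67 | 54 | 0.80 / 0.66 | 50.4% / 67.2% | 72 / 48 |
| 0.5 | 0.77 | 47 | 0.68 / 0.60 | 64.5% / 75.5% | 52 / 40 |
| 0.65 | 0.85 | 42 | 0.57 / 0.52 | 79.6% / 85.5% | 38 / 32 |
| 0.8 | 0.93 | 39 | 0.43 / 0.41 | 95.8% / 96.8% | 22 / 22 |
| 0.9 | 0.98 | 37 | 0.30 / 0.30 | above 99% for both | – |

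Simulation (40,000 trials per r) gave variance ratios of 0.668, 0.777, 0.854, 0.926 and 0.980, and both estimators averaged 0.80 for a true 0.80. With equal SDs, break-even is at r = 2/1.031 − 1 = 0.94.

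**5. If 0.2 is literally a between-group d.** Over r = 0.3 to 0.9, power is 8% to 26% with change scores and 9% to 26% with ANCOVA. The choice of model adds at most about 1.5 points.

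**6. Unequal SDs, post/pre ratio k.** The ratio becomes k²(1−r²)·1.031/(1+k²−2rk).

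- k = 1.25: 0.81, 0.92, 0.99 and 1.03 at r = 0.3, 0.5, 0.65 and 0.8.
- k = 0.8: between 0.52 and 0.66 over r = 0.3 to 0.9.

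Since (1+k²−2rk) − k²(1−r²) = (1−rk)², which is never negative, the ratio cannot exceed 1.031. The worst case is rk = 1, where the change score already uses the right slope; k = 1.25 with r = 0.8 is exactly that case.

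**7. The same loss seen conditionally.** The baseline difference between arms has SD √(2/18) = 0.333, so a chance gap above 0.5 SD has probability P(|Z| > 1.5) = 0.134. A gap of 0.5 SD shifts the change-score estimate by 0.5(1−r), which is 0.25 SD at r = 0.5. This is not a second defect.

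**The case against.** The planned interaction test is valid and matches the test the trial was sized on, so choosing ANCOVA over it could be called preference. The size of the gain cannot be established from the documents, since it needs both r and the SD ratio. The largest gains also fit the plan's own N poorly: at r = 0.3 with f = 0.2 the planned test needs 72 women, not 36. At the values of r that do recover N = 36, the gain is moderate (about 80% to 86% power near r = 0.65, f = 0.2) or negligible (variance ratio about 0.985 near r = 0.91, f = 0.1). Finally, the plan's failure to name the treatment term arguably matters more, and could be repaired without ANCOVA.

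Most of this stands as qualification. The r = 0.3 row should not be read as what this plan implies, and no single figure for the gain should be quoted. The powers rest on normality, while the analysis section itself allows for skewed outcomes. Naming the interaction would indeed settle which term is the treatment test.

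None of it removes the point. The possible loss is bounded at about 3% of variance, while the possible gain is much larger over a wide range of r, from data the trial will hold anyway.

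**Conclusion.** The point holds as an efficiency improvement that should be made; the planned interaction test is not wrong. With equal SDs and 18 per arm, ANCOVA removes about 15% of the variance at r = 0.65 (14.9% before rounding), about 23% at r = 0.5 and 33% at r = 0.3. The gain is small at r = 0.8 or above, and with equal SDs it turns into a trivial loss above about r = 0.94. If the post SD is 25% larger than the pre SD, the gain is nearly gone at r = 0.65. If 0.2 really is a between-group d, power is low under either model and ANCOVA does not rescue it.

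The algebra is certain; the benefit in this trial is not, because neither r nor the SDs are given. The statement that the planned test is valid applies to the interaction, which the sample-size section uses but the analysis section does not name.

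**What to change.** Add to the Statistical Analysis section, before outcome data are examined by arm:

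*For fatigue, urinary incontinence symptoms, sexual function and quality of life, the between-group effect will be estimated by ANCOVA with the post-intervention score as response, group as factor and the baseline value of the same outcome as covariate. The adjusted HEG minus CEG difference with its 95% CI is the basis for the conclusion, rather than the time or group main effect.*

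Keep the mixed ANOVA as a supporting analysis. The wording also settles which estimate carries the treatment claim.

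The cost is one or two sentences and one degree of freedom (33 instead of 34), plus an estimated slope whose average penalty is 1/32 of the variance. No new data or visits are needed, and SPSS, already named in the plan, fits the model.

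### The two-time-point mixed ANOVA is a change-score comparison among women with both assessments; adjusting the post score for baseline is more precise and avoids bias from baseline-related dropout

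*Combined protocol and SAP*

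**What the plan says.** The Statistical Analysis section names one method for all four outcome domains: "a two-way mixed analysis (two-way ANOVA) will be performed, considering time (pre-intervention and post-intervention) as an intra-subject" factor, and group as the between-subjects factor. It adds "The significance level will be set at .05 for all statistical analyses". The software is SPSS 17.0; the procedure within it is not named.

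The Determination of sample size section used a repeated-measures ANOVA, "considering interaction between and within groups using 2 measurements", with an effect size labelled Cohen's d "of 0.2, to achieve a power of 80" per cent at the 5% level. The result: "Thirty-six participants (18 per group) were suggested". No pre-post correlation and no allowance for loss are given.

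Under Generation and hiding of sequences, randomisation follows the baseline evaluations. Every randomised woman should therefore have a pre-test, and any loss falls on the post-test. No section states an analysis population, a rule for missing data or an expected dropout rate.

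**The concern.** In a two-by-two mixed ANOVA, the F test of the interaction is the square of the t test on change (post minus pre) between groups. Two consequences follow.

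- **Precision.** A change score subtracts the whole baseline, whatever the correlation. Regression on baseline subtracts only the part that predicts the post score, so its error variance is lower whenever the correlation is below 1.
- **Bias under selective loss.** If one arm loses more of its severely affected women, the women left there start better than the other arm. Regression to the mean then moves their change score, and the contrast shifts with no treatment effect present. The shift works against the arm that lost its worst cases. Baseline adjustment corrects for this.

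At stake are power in a trial of 36 women and the validity of the group comparison if losses differ by arm. Baseline is already collected before randomisation, so the better analysis needs no new data.

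**Working it through.** **Inputs from the documents:** 36 women, 18 per arm; two-sided 5% level; 80% power; two measurements; effect size 0.2. **Assumptions, because the documents are silent:** pre-post correlation ρ (0.5 as base, range shown), equal SD at both times, and every dropout pattern below.

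**1. The plan's own figure.** For the within-between interaction, λ = N·m·f²/(1−ρ) with m = 2, on 1 and N−2 degrees of freedom. With two groups, d = 0.2 corresponds to f = 0.1.

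- f = 0.2, ρ = 0.5: λ = 36 × 2 × 0.04/0.5 = 5.76, power 64.5%; 80% needs 52 women.
- f = 0.1, ρ = 0.5: λ = 36 × 2 × 0.01/0.5 = 1.44, power 21%; 80% needs 200 women.
- 36 is returned only if ρ is about 0.654–0.674 (f = 0.2) or 0.914–0.918 (f = 0.1). Neither value is stated.

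The 80% is therefore not reproduced. Steps 2 and 3 take it as given, only to show how power moves.

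**2. Planned ANOVA with fewer pairs.** 80% power with 36 pairs requires λ = 8.32. This is f = 0.240 at ρ = 0.5, or a difference in change of √(4 × 8.32/36) = 0.96 SD of change. For the same effect, λ scales with N:

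| Pairs | λ | Power |
|---|---|---|
| 36 | 8.32 | 80.0% |
| 32 | 7.39 | 74.9% |
| 30 | 6.93 | 72.0% |
| 28 | 6.47 | 68.7% |

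These powers do not depend on which f and ρ were entered, because they are tied to the stated 80%.

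**3. Baseline adjustment with the same pairs.** In units of the score variance, the error variance is 2(1−ρ) for change and 1−ρ² for ANCOVA. The ratio is (1+ρ)/2, so λ is multiplied by 2/(1+ρ), with N−3 error degrees of freedom. For 30 pairs:

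- ρ = 0.5: λ = 6.93 × 1.333 = 9.24, power 83%.
- ρ = 0.8: λ = 6.93 × 1.111 = 7.70, power 76%.

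Allowing for chance baseline imbalance takes off about one point (82% and 75%). The planned ANOVA gives 72%.

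**4. Bias illustration.** Simulation of 20,000 trials: 18 per arm, normal scores, no treatment effect, and the 4 worst baseline scores removed from one arm only.

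| ρ | Change-score contrast | ANCOVA, same women |
|---|---|---|
| 0.5 | 0.18 SD | 0.000 SD |
| 0.7 | 0.11 SD | 0.002 SD |

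The change-score bias equals (1−ρ) times the baseline shift between the arms' remaining women. That shift is about 0.36 SD: 0.5 × 0.36 = 0.18 and 0.3 × 0.36 = 0.11.

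Milder patterns at ρ = 0.5:

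- 4 lost from one arm, with the chance of loss rising with baseline by a factor of 2.7 or 1.65 per SD: about 0.1 or 0.06 SD.
- 4 lost from one arm and 2 from the other: 0.05 SD or less.
- The same loss in both arms: 0.

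At ρ = 0.7 these are 0.3/0.5 = 0.6 times as large.

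**5. Bias against the effect.** At ρ = 0.5 the SD of change equals the SD of the score, so 0.18/0.96 = 19% of the effect that 36 pairs detect with 80% power. At ρ = 0.7 that effect is 0.96 × √0.6 = 0.74 score SD, and 0.11/0.74 = 15%.

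**The case against.** The strongest reply is that the plan is silent, not wrong: it never announces a completers-only analysis, it gives no sign that dropout will be heavy or one-sided, and its larger power problem exists with no loss at all. Much of this stands, and it rules out several stronger readings.

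- **That the fault lies in the analysis set.** The documents name no set; complete pairs follow by default from a classical repeated-measures procedure. The ANCOVA with no bias in step 4 was fitted to the same completers, so the fault shown is the change-score contrast.
- **That the bias is about as large as the planned effect.** This needs the 0.2 to be read as 0.2 SD on change. Then λ = 9 × 0.04 = 0.36 and 36 women have about 9% power, so there is no 80% to lose. The same effect cannot serve both the power figures and that comparison. The loss pattern is also extreme.
- **That the plan cannot hold 80% power.** The fall is conditional and gradual, about 1 to 1.5 points per woman lost.
- **That differential dropout is likely because one arm has extra exercises.** The Hypopressive Exercise Protocol section does add work in one arm, but no figure links it to dropout.
- **That a mixed model rescues women without a post-test.** ANCOVA omits them. A mixed model keeps their baseline but recovers little from it. Neither protects against dropout driven by the unseen post score.

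The objection does not reach the choice of contrast. Baseline adjustment uses data already collected, is more precise over the correlations examined, and removes one identifiable source of bias.

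**Conclusion.** The point holds as a choice of analysis. As written, the group comparison is a change-score contrast on complete pairs. Against baseline adjustment it gives up about 4 to 11 points of power with 30 pairs (72% against 76% at correlation 0.8 and 83% at 0.5), if 36 pairs truly gave 80%. It is open to bias when dropout depends on baseline severity differently by arm: 0.18 or 0.11 SD in the illustrative extreme, 15–19% of the effect that 36 pairs would detect with 80% power, and near zero when losses are balanced.

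The power comparison rests on equal SDs at the two times, a common slope on baseline and the stated 80%. The bias figures rest on assumed loss patterns, and adjustment removes only the part explained by baseline. The sample-size basis is a separate and larger uncertainty.

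**What to change.** - **Statistical Analysis.** For each outcome, make the group comparison an ANCOVA of the post score on group and baseline score, or a mixed model with a common baseline mean. Analyse women in their randomised group and report the adjusted difference with its 95% confidence interval. State that ANCOVA omits women with no post-test.
- **Data collection.** Seek the post-test from women who stop training, and report losses by arm with their baseline scores. This is the main safeguard against dropout that baseline does not explain.
- **Determination of sample size.** State that 36 means women with both assessments and that power falls with loss. Give the effect-size metric (d or f) and the assumed correlation, and recompute. Until then do not restate 80% as correct: at correlation 0.5, 36 women give 64.5% for f = 0.2 and 21% for f = 0.1.

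The cost is protocol wording, a few extra contacts for post-tests, and a power statement that may prove less favourable. The change of analysis itself needs no extra participants or measurements.

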**Figure 1.**

### **Protocol of therapeutic exercise**

Both groups of exercises will train three times a week, twice in a synchronous online way and once in an asynchronous way, considering a standardized exercise guide. In all of the intervention sessions, the conventional exercises will be guided by the standardized exercise guide previously developed by the team of the study for 4 weeks. Each session will last approximately 60 minutes. In all sessions, exercise perception (using the Borg scale), respiratory rate and heart rate will be monitored, considering instructions via remote. For aerobic training, a light to moderate intensity will be considered (Borg 9-13). Resistance exercises will be carried out using large muscle groups and the participants' body weight. All the exercise sessions will be the same for the groups and will begin with a five-minute warm-up with exercises that involve large muscle groups in a perceived exercise rating of 10 to 12 on the Borg scale and the sessions conclude with a 10 minutes that include dynamic and static muscle stretching activities of the main muscle groups worked in the session. In the first week of training, a familiarization with the perception of perceived effort will be carried out using the Borg scale.

The strength training will consist of 3 sets of 8-12 repetitions of 8 exercises, using leg extensions and lower limbs, biceps curls and extensions, lunges, chest curls, abdominal curls, shoulder curls and back extension. Participants will perform exercises without charge in all sessions. The training progress will be related to the increase in volume according to what corresponds to each week: a) weeks 1 and 2 (3 sets of 8 repetitions, adaptation weeks), b) week 3 (3 sets of 10 repetitions) and c) week 4 (3 sets of 12 repetitions).

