### **Hypopressive Exercise Protocol**

The hypopressive exercises will be carried out by the GEH group at the end of the strength and resistance training session. It will be considered the static hypopressive exercise in the supine position, with a variant of arms in flexion, abduction and extension, consisting of 3 exercises. The dosage will consist of 3 series of each exercise, using a protocol adapted from the previous study by Cabañas and Chapinal. Participants must perform 3 cycles of deep inspiration (nose) and forced breathing (mouth). After the last breath, the participants will be instructed to maintain the position performing 3 cycles of normal breathing, without performing the apnea, to guarantee the safety of the user and that the intervention is remote. During the breathing phase, participants will be instructed to perform pelvic floor contraction. The procedure must be repeated 3 times in each variant of arms.

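### The only planned outcome effect size is each arm's own pre-post Cohen's d; no HEG minus CEG difference with a 95% CI is pre-specified

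*Combined protocol and SAP*

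**What the plan says.** The Statistical Analysis section sets one model, a mixed ANOVA, for all four outcomes. Its factors are given as follows: "considering time (pre-intervention and post-intervention) as an intra-subject and group factor as a between-subjects factor". It does not say which term of that model (time, group or their interaction) answers the trial question. The interaction appears only under Determination of sample size, where the calculation is described as "considering interaction between and within groups using 2 measurements".

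On magnitude, the Statistical Analysis section says: "The intragroup effect sizes for the aforementioned variables will also be calculated using the Cohen d index". The next sentence gives the labels: "An effect size of more than 0.8 will be considered large, approximately 0.5 moderate, and less than 0.2 small". The denominator of d is not defined.

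The 95% confidence limits in that section are listed with the mean and SD as one way of expressing the data, the alternative being the median and quartiles. They are descriptive and are not tied to a difference between arms. No section plans a difference between the hypopressive group (HEG) and the conventional group (CEG), or an interval for one.

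On what separates the arms, Protocol of therapeutic exercise says "All the exercise sessions will be the same for the groups", and Hypopressive Exercise Protocol says "The hypopressive exercises will be carried out by the GEH group at the end of the strength and resistance training session". I read GEH there as the group called HEG elsewhere.

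**The concern.** The randomised question is what hypopressive exercise adds to training that both arms receive. A within-arm pre-post d answers a different question: how much women in one arm changed over four weeks, from whatever cause. Shared training, time and regression to the mean all enter it, and randomisation protects none of these. The d can be moderate or large in both arms when the add-on does nothing. Setting the two values side by side gives neither a between-group estimate nor a measure of its precision.

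The ANOVA supplies a between-group p-value but no magnitude. In a trial of this size the most useful result may be the range of add-on effects that the data still allow, and the plan does not require that range to be reported.

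**Working it through.** **Inputs from the document.** Two arms, 18 per group and two measurements (Determination of sample size); significance level 0.05 (Statistical Analysis). The document does not say whether tests are two-sided; I assume they are.

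**Assumptions.** Outcome SD of 1 at both times in both arms, normal data, no dropout, and pre-post correlation r = 0.5, 0.65 or 0.8. The document gives no correlation.

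**The plan's own figure.** The plan gives no figure for the arm difference. Its one related figure is N = 36. For the interaction F test, the noncentrality is f² × N × 2/(1 − r). Reading 0.2 as f with r = 0.66 gives 0.04 × 36 × 2/0.34 = 8.47 and 80.7% power, and 36 is then the smallest even N reaching 80%. Reading 0.2 as Cohen's d (f = 0.1) with r = 0.5 gives N = 200. So 36 depends on an unstated correlation and on how 0.2 is read. That is a separate matter; 18 per arm is taken as given below.

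**Step 1: what the within-arm d estimates.** Let s be the shared mean change, a the add-on effect and k the denominator. Then d is (s + a)/k in HEG and s/k in CEG, while the randomised contrast is a. Take s = 0.5 SD and a = 0.
- With k = the SD at one time point, d is 0.50 in each arm.
- With k = the SD of change, √(2(1 − r)) = 1.00, 0.837, 0.632, d is 0.50, 0.60, 0.79 in each arm.

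The contrast is zero throughout. At r = 0.8 the choice of denominator alone moves d from 0.50 to 0.79, that is, from the moderate label to just under the large one.

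**Step 2: precision of the contrast.** For the difference in change, the half-width is t(0.975, 34) × √(2(1 − r)) × √(2/18). For the baseline-adjusted (ANCOVA) difference it is t(0.975, 33) × √(1 − r²) × √(2/18). The t values are 2.032 and 2.035, and √(2/18) = 0.333.

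| r | Difference in change | Baseline-adjusted |
|---|---|---|
| 0.5 | 0.677 SD | 0.587 SD |
| 0.65 | 0.567 SD | 0.515 SD |
| 0.8 | 0.428 SD | 0.407 SD |

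**Step 3: what a non-significant interaction leaves open.** The interaction is non-significant when the observed difference is smaller in size than the half-width h. The upper limit still reaches 0.5 SD when the observed difference is at least 0.5 − h. Both hold for observed differences from −0.18 to 0.68 (r = 0.5), −0.07 to 0.57 (r = 0.65) and 0.07 to 0.43 (r = 0.8). For example, an observed difference of 0.2 SD at r = 0.65 has SE 0.837 × 0.333 = 0.279, F = (0.2/0.279)² = 0.51, p = 0.48 and 95% CI −0.37 to 0.77.

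**Step 4: why naming the term is worth a sentence.** If both arms gain 0.5 SD and do not differ, the noncentrality of the time effect at r = 0.5 is 0.5/√(2 × 0.5/36) = 3.0. It is then significant with 83.0% probability, so a significant ANOVA term need not concern the add-on.

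**The case against.** There is a fair case that this is a small matter, and much of it stands.

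- **The interaction is already implied.** A reader might infer that the plan lacks a between-group test. The document does not support that: the trial is sized on the interaction, the matching mixed ANOVA is planned, and this is one combined protocol and SAP. What remains is that the analysis section does not designate the term.
- **The d is supplementary.** A reader might infer that the trial will draw its conclusion from the within-arm d. The text says only that it is also calculated, and no section attaches a decision to it.
- **A between-group interval may be recoverable.** A reader might infer that it could be rebuilt only from the interaction F or an exact p-value. That is too strong. If d uses the SD of change, that SD is the mean change divided by d, and the standard error of the difference in change follows, subject to rounding. For outcomes summarised by mean and SD, the post-intervention difference and its interval also follow directly, with a half-width of about 0.68 SD (2.032 × 0.333). What remains is that the plan commits neither to printing a between-group interval nor to a denominator that allows the first route.
- **The labels are not cut-offs.** A reader might infer that the labels will often set the two arms apart when there is no add-on effect. How often depends almost wholly on where the true shared gain sits relative to an assumed threshold, and the plan describes moderate as approximately 0.5. No such frequency is relied on here.

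**Conclusion.** The point holds as a specification and reporting gap that should be fixed; it does not threaten the trial's validity. The one effect measure the plan names for its outcomes, and the labels that follow it, describe change within each arm. No estimate or interval is pre-specified for the contrast that was randomised.

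The practical size is the imprecision that could go unreported: roughly 0.4 to 0.7 SD either side of the estimate with 18 per arm. A moderate add-on effect would often remain compatible with a non-significant result. These widths rest on the assumed correlations of 0.5 to 0.8, equal SDs and full follow-up; at a correlation of 0 or 0.9 the half-width would be 0.96 or 0.30 SD. The reading of the text does not depend on those assumptions.

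**What to change.** In the Statistical Analysis section:

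1. State that the group-by-time interaction is the test of the hypopressive effect.
2. For each outcome analysed by the ANOVA, report the HEG minus CEG difference in change with its 95% CI, in scale units and standardised (for example by the pooled baseline SD). This interval matches the interaction test.
3. Apply the magnitude labels to that between-group figure.
4. Keep the within-arm d as descriptive only, and state its denominator.

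Optionally, pre-specify a baseline-adjusted (ANCOVA) difference as the single between-group analysis, for its somewhat narrower interval. Both the p-value and the CI should then come from that model.

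The cost is one to three sentences and slightly more reporting. The data collected and the sample size do not change.
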